9.6. Pharmacodynamics

Samples for pharmacodynamic analysis will not be collected in this study.

9.7. Pharmacogenomics/Genetics

Samples for pharmacogenomics or genetics will not be collected in this study.

9.8. Health Economics

Not applicable.

10. Statistical Considerations

10.1. Sample Size Determination

Approximately 210 patients may be enrolled in a 1:1 ratio to LY3127804 or placebo (105 per treatment group) in order that 200 patients complete the study. A sample size of 100 in each group will have 81% power to detect a difference between the placebo group and the LY3127804 group using a Wilcoxon rank-sum test with a 0.05 one-sided significance level. This powering is based on the following assumptions: IMV rate of 25% and mortality rate of 12.5% in the placebo group, 50% improvement in IMV rate and mortality rate for the LY3127804 group relative to placebo, and a mean difference (LY3127804 minus placebo) of 3.0 ventilator-free days where patients who die are assigned a value of -1.

Randomization will be stratified by age group (<65 years and ≥65 years), sex, and site.

10.2. Populations for Analyses

For purposes of analysis, the following populations are defined:

Population	Description
Enrolled Set	All patients who sign informed consent
Efficacy Analysis Set	All randomized patients who take at least 1 dose of double-blind study treatment. Patients will be included in the treatment group they were randomized.
Safety Analysis Set	All randomized patients who take at least 1 dose of double-blind study treatment. Patients will be analyzed according to the treatment they actually received.

10.3. Statistical Analyses

10.3.1. General Statistical Considerations

Statistical analysis of this study will be the responsibility of Lilly or its designee. A detailed statistical analysis plan (SAP) describing the statistical methodologies will be developed.

Efficacy analyses will be conducted on the Efficacy Analysis Set; safety analyses will be conducted on the Safety Analysis Set.

Descriptive statistics will include the number of patients, mean, standard deviation, median, minimum, and maximum for continuous measures, and frequency counts and percentages for categorical measures.

Investigators with fewer than 2 randomized patients per treatment group will be pooled for statistical analysis purposes. Sensitivity analyses accounting for missing data will be described in the SAP.

Unless otherwise noted, treatment comparisons of discrete variables will be made using logistic regression analysis with treatment and randomization stratification variables in the model. The percentages, difference in percentages, and 95% confidence interval (CI) of the difference in percentages will be reported.

Unless otherwise noted, treatment comparisons of continuous variables will be made using a restricted maximum likelihood-based mixed-effects model of repeated measures (MMRM). The model will include treatment, age group, and site, and, if applicable, study day and treatment-by-study day interaction as fixed categorical effects. Additional details on the MMRM analyses will be described in the SAP.

All tests of treatment effects will be conducted at a 1-sided alpha level of 0.05, unless otherwise stated.

Any change to the data analysis methods described in the protocol will require an amendment ONLY if it changes a principal feature of the protocol. Any other change to the data analysis methods described in the protocol, and the justification for making the change, will be described in the clinical study report (CSR). Additional exploratory analyses of the data will be conducted as deemed appropriate.

10.3.2. Patient Comparability

10.3.2.1. Patient Disposition

A detailed description of patient disposition will be provided at the end of the study. Reasons for discontinuation will be summarized by treatment group.

10.3.2.2. Patient Characteristics

Demographic and baseline characteristics will be described. No statistical comparisons between treatment groups will be made.

10.3.2.3. Concomitant Therapy

Concomitant medications will be summarized for patients who enter each treatment period and will be presented by anatomical therapeutic chemical drug classes using the latest version of the WHO drug dictionary.

10.3.3. Efficacy Analyses

10.3.3.1. Primary Analyses

The Wilcoxon rank-sum analysis of the primary endpoint, death at day 28 and days free of mechanical ventilation within 28 days among survivors (VFDsurv), will use a scoring scheme with patients from the Efficacy Analysis Set who do better getting a higher score. We will assign a VFDsurv score of -1 to patients who die before 28 days. For those patients who survive to day 28 the VFDsurv score will be equal to the number of VFDs calculated according to the above definition. If a patient is discharged from the hospital before day 28, and if the patient is still alive at day 28, they will be credited with ventilator free days from the time of discharge until day 28. The statistical method for this endpoint will be based on the van Elteren test adjusting for the randomization stratification factors (age group, sex, and site).

10.3.3.2. Secondary Analyses

Secondary end points will be described and compared between treatment groups. The NIAID ordinal scale and length of hospitalization will be analyzed with the Wilcoxon rank-sum test.

Mortality, survival without respiratory failure, and categorical changes on the NIAID ordinal scale will be analyzed as discrete variables.

10.3.3.3. Exploratory Analyses

Pulmonary function will be analyzed via MMRM analysis.

10.3.4. Safety Analyses

Safety will be assessed by evaluating all reported AEs and changes in laboratory analytes, ECGs, and vital signs (including body weight) in the Safety Analysis Set and summarized by treatment group.

Duration of exposure to therapy will be calculated for each patient.

AEs will be coded according to the Medical Dictionary for Regulatory Activities and summarized by system organ class, preferred term, severity, and relationship to investigational product. A TEAE is defined as an event that first occurred or worsened in severity after baseline. In the analysis of TEAEs, all preexisting conditions recorded before the first dose of study drug will be used as baseline. For each event classification term, the number of patients experiencing a TEAE with that classification term will be tabulated. Treatment-related TEAEs are defined as events that are indicated by the investigator on the eCRF to be related to treatment. If a patient reports the occurrence of a particular event more than once, the most severe of those events will be included in the summary tables of TEAEs, and the most severe of the most related of those events will be included in the summary tables of treatment-related events.

Additional safety parameters include laboratory test results, ECGs, and vital-sign measurements. The baseline for computing the change in safety data is the last value collected before the first dose of study drug. The parameters will be listed and summarized with standard descriptive statistics. Change from baseline will also be summarized.

10.3.5. Other Analyses

10.3.5.1. Subgroup Analyses

Subgroup analyses of the primary analysis will be conducted on relevant subgroups, including patients who are confirmed SARS-CoV-2 positive, age group, and sex.

10.3.6. Interim Analyses

An interim analysis may be conducted to assess efficacy results. The interim efficacy results may be used for internal decision-making to trigger planning activities associated with the investigational product and/or to assess futility. No adjustment of Type I error will be performed as the study will not be stopped for efficacy, and no modification of Study UDAA is expected based on these interim results, other than possibly stopping the study for futility. The assessment would be conducted by a sponsor assessment committee with a limited number of preidentified team members who do not have direct site contact or data entry/validation responsibilities. Unblinding details will be specified in the unblinding plan section of the SAP or in a separate

unblinding plan document. Information that may unblind the study during the analyses will not be reported to study sites or to the blinded study team until the study has been unblinded.

An independent DMC will review unblinded safety data on an ongoing basis (Section [9.4.5](#)). Details are specified in the DMC Charter.

Ongoing monitoring of safety data (including AEs, SAEs, and selected laboratory measurements) will continue throughout the study by the sponsor using blinded data.

11. References

- [NCT02597036] ClinicalTrials.gov [Internet]. Bethesda (MD): National Library of Medicine (US). Identifier NCT02597036, A Study of LY3127804 With Ramucirumab in Participants With Advanced Solid Tumors; 2019 Nov 19 [cited 2020 Apr 08]; Available from: <https://clinicaltrials.gov/ct2/show/NCT02597036>
- [NCT04280705] ClinicalTrials.gov [Internet]. Bethesda (MD): National Library of Medicine (US). Identifier NCT04280705, Adaptive COVID-19 Treatment Trial (ACTT); 2020 Apr 06 [cited 2020 Apr 08]; Available from: <https://clinicaltrials.gov/ct2/show/NCT04280705>

Appendix 1. Abbreviations and Definitions

Term	Definition
AE	adverse event: Any untoward medical occurrence in a patient or clinical investigation patient administered a pharmaceutical product that does not necessarily have a causal relationship with this treatment. An adverse event can therefore be any unfavorable and unintended sign (including an abnormal laboratory finding), symptom, or disease temporally associated with the use of a medicinal (investigational) product, whether or not related to the medicinal (investigational) product.
ALT	alanine aminotransferase
Ang2	angiopoietin 2
ARDS	Acute respiratory distress syndrome
AST	aspartate aminotransferase
Blinding	A double-blind study is one in which neither the patient nor any of the investigator or sponsor staff who are involved in the treatment or clinical evaluation of the patients are aware of the treatment received.
complaint	A complaint is any written, electronic, or oral communication that alleges deficiencies related to the identity, quality, purity, durability, reliability, safety or effectiveness, or performance of a drug or drug delivery system.
compliance	Adherence to all study-related, good clinical practice (GCP), and applicable regulatory requirements.
CFR	case fatality rate
COVID-19	coronavirus disease
CI	confidence interval
CRP	clinical research physician: Individual responsible for the medical conduct of the study. Responsibilities of the CRP may be performed by a physician, clinical research scientist, global safety physician or other medical officer.
DMC	data monitoring committee
ECG	electrocardiogram
ECMO	extracorporeal membrane oxygenation
eCRF	electronic case report form
ED	early discontinuation
EDC	electronic data capture

enroll	The act of assigning a patient to a treatment. Patients who are enrolled in the study are those who have been assigned to a treatment.
enter	Patients entered into a study are those who sign the informed consent form directly or through their legally acceptable representatives.
FT4	free thyroxine
FU	follow-up
GCP	good clinical practice
GPS	Global Patient Safety
HIV	Human immunodeficiency virus
IB	Investigator's Brochure
ICF	informed consent form
ICH	International Council for Harmonisation
ICU	intensive care unit
IMV	intermittent mandatory ventilation
Informed consent	A process by which a patient voluntarily confirms his or her willingness to participate in a particular study, after having been informed of all aspects of the study that are relevant to the patient's decision to participate. Informed consent is documented by means of a written, signed and dated informed consent form.
IV	intravenous
IWRS	interactive web-response system
mAb	monoclonal antibody
MMRM	mixed-effects model of repeated measures
NCI-CTCAE	National Cancer Institute Common Terminology Criteria for Adverse Events
NIAID	National Institute of Allergy and Infectious Diseases
PK/PD	pharmacokinetics/pharmacodynamics
QTc	corrected QT interval
Q2W	every two weeks
SAE	serious adverse event
SAP	statistical analysis plan

Screen	The act of determining if an individual meets minimum requirements to become part of a pool of potential candidates for participation in a clinical study.
SpO₂	oxygen saturation
SUSARs	suspected unexpected serious adverse reactions
TEAE	Treatment-emergent adverse event: An untoward medical occurrence that emerges during a defined treatment period, having been absent pretreatment, or worsens relative to the pretreatment state, and does not necessarily have to have a causal relationship with this treatment.
TSH	thyroid stimulating hormone
VFD	ventilator free days
VFDsurv	ventilator free days among survivors
WBC	white blood cell

Appendix 2. Clinical Laboratory Tests

Clinical Laboratory Tests

Hematology

Hemoglobin
 Hematocrit
 Erythrocyte count (RBC)
 Mean cell volume
 Mean cell hemoglobin concentration
 Leukocytes (WBC)
 Neutrophils, segmented
 Lymphocytes
 Monocytes
 Eosinophils
 Basophils
 Platelets

COVID-19 Panel

D-dimer
 Cardiac troponin (I or T)
 LDH
 C-reactive protein
 Procalcitonin
 Ferritin
 IL-6
 BNP

Clinical Chemistry**Serum Concentrations of:**

Sodium
 Potassium
 Total bilirubin
 Direct bilirubin
 Alkaline phosphatase
 Alanine aminotransferase (ALT)
 Aspartate aminotransferase (AST)^a
 Blood urea nitrogen (BUN)
 Creatinine
 Uric acid
 Calcium
 Glucose (random)
 Albumin
 Creatine kinase (CK)
 Total protein

Pregnancy Test (females only)**Thyroid Function Test**

Free thyroxine (fT4)
 Thyroid stimulating hormone (TSH)

Influenza/RSV/Respiratory Viral Panel^b

Abbreviations: BNP = brain natriuretic peptide; IL-6 = interleukin 6; LDH = lactate dehydrogenase; RBC = red blood cells; RSV = respiratory syncytial virus; WBC = white blood cells.

- a For purposes of this study, if AST is not routinely reported when ALT is normal, then AST is not required.
 b Viral testing is only performed for patients who have undetermined or negative COVID-19 test(s). Viral testing is per the institution's testing guidelines.

Appendix 3. Study Governance Considerations

Appendix 3.1. Regulatory and Ethical Considerations, Including the Informed Consent Process

Appendix 3.1.1. Informed Consent

The investigator is responsible for:

- ensuring that the patient understands the nature of the study, the potential risks and benefits of participating in the study, and that their participation is voluntary.
- ensuring that informed consent is given by each patient or legal representative. This includes obtaining the appropriate signatures and dates on the informed consent form (ICF) prior to the performance of any protocol procedures and prior to the administration of investigational product.
- answering any questions the patient may have throughout the study and sharing in a timely manner any new information that may be relevant to the patient's willingness to continue his or her participation in the study.
- ensuring that a copy of the ICF is provided to the patient or the patient's legal representative and is kept on file.
- ensuring that the medical record includes a statement that written informed consent was obtained before the patient was enrolled in the study and the date the written consent was obtained. The authorized person obtaining the informed consent must also sign the ICF.

Appendix 3.1.2. Recruitment

Lilly or its designee is responsible for the central recruitment strategy for patients. Individual investigators may have additional local requirements or processes.

Investigator(s) will be responsible for patient recruitment through local requirements or processes.

Appendix 3.1.3. Ethical Review

The investigator or an appropriate local representative must give assurance that the ethical review board (ERB) was properly constituted and convened as required by International Council for Harmonisation (ICH) guidelines and other applicable laws and regulations.

Documentation of ERB approval of the protocol and the ICF must be provided to Lilly before the study may begin at the investigative site(s). Lilly or its representatives must approve the ICF, including any changes made by the ERBs, before it is used at the investigative site(s). All ICFs must be compliant with the ICH guideline on Good Clinical Practice (GCP).

The study site's ERB(s) should be provided with the following:

- the protocol and related amendments and addenda, current Investigator Brochure (IB) and updates during the course of the study
- informed consent form
- other relevant documents (for example, curricula vitae, advertisements)

Appendix 3.1.4. Regulatory Considerations

This study will be conducted in accordance with the protocol and with the:

- consensus ethics principles derived from international ethics guidelines, including the Declaration of Helsinki and Council for International Organizations of Medical Sciences (CIOMS) International Ethical Guidelines
- applicable ICH GCP Guidelines
- applicable laws and regulations

Some of the obligations of the sponsor will be assigned to a third party.

Appendix 3.1.5. Investigator Information

Physicians with a specialty in pulmonology and/or intensive care and/or other identified critical care staff will participate as investigators in this clinical trial.

Appendix 3.1.6. Protocol Signatures

The sponsor's responsible medical officer will approve the protocol, confirming that, to the best of his or her knowledge, the protocol accurately describes the planned design and conduct of the study.

After reading the protocol, each principal investigator will sign the protocol signature page and send a copy of the signed page to a Lilly representative.

Appendix 3.1.7. Final Report Signature

The sponsor's responsible medical officer and statistician will approve the final CSR for this study, confirming that, to the best of his or her knowledge, the report accurately describes the conduct and results of the study.

Appendix 3.2. Data Quality Assurance

To ensure accurate, complete, and reliable data, Lilly or its representatives will do the following:

- provide instructional material to the study sites, as appropriate
- sponsor start-up training to instruct the investigators and study coordinators. This training will give instruction on the protocol, the completion of the CRFs, and study procedures.
- review study data remotely where possible

- be available for consultation and stay in contact with the study site personnel by mail, telephone, and/or electronic mail
- review and evaluate CRF data and use standard computer edits to detect errors in data collection
- conduct a quality review of the database

In addition, Lilly or its representatives will periodically check a sample of the patient data recorded against source documents at the study site. The study may be audited by Lilly or its representatives, and/or regulatory agencies at any time. Investigators will be given notice before an audit occurs. This may be virtual as current sites are not allowing monitors on site to reduce the risk of COVID-19 contamination.

The investigator will keep records of all original source data. This might include laboratory tests, medical records, and clinical notes. If requested, the investigator will provide the sponsor, applicable regulatory agencies, and applicable ERBs with direct access to original source documents.

Appendix 3.2.1. Data Capture System

An EDC system will be used in this study. The site maintains a separate source for the data entered by the site into the sponsor-provided electronic data capture system.

Case report form data will be encoded and stored in a clinical trial database.

Appendix 3.3. Study and Site Closure

Appendix 3.3.1. Discontinuation of Study Sites

Study site participation may be discontinued if Lilly or its designee, the investigator, or the ERB of the study site judges it necessary for medical, safety, regulatory, or other reasons consistent with applicable laws, regulations, and GCP.

Appendix 3.3.2. Discontinuation of the Study

The study will be discontinued if Lilly or its designee judges it necessary for medical, safety, regulatory, or other reasons consistent with applicable laws, regulations, and GCP.

Appendix 3.4. Publication Policy

The publication policy for Study UDAA is described in clinical trial agreement.

Appendix 4. Sampling Summary

This table summarizes the approximate number of samples [venipunctures, blood draws from lines, urine] and volumes for all sampling [screening, standard of care laboratory,] and tests during the study. Fewer samples may actually be taken, but this will not require a protocol amendment.

Protocol I7W-MC-UDAA Sampling Summary

Purpose	Sample Type	Maximum Amount per Sample	Maximum Number Samples	Maximum Total Amount
Hematology and Chemistry (most are stand of care samples) ^a	Blood	3-6 mL	7	21-42 mL
Pregnancy Test (blood or urine)	Blood/ urine	3 mL blood or urine sample	2	6 mL blood or urine sample
Thyroid Function Test and Covid Panel (Appendix 2)	Blood	8.5 mL	3	25.5 mL

^a Based on laboratory safety values, unscheduled hepatic monitoring testing may be performed as part of patient follow-up, in consultation with Lilly-designated Medical Monitor.

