Randomization will be stratified by age group (<65 years and \geq 65 years), sex and site.

Secondary efficacy analyses will assess secondary endpoints as well as analyses of relevant subgroups.

Safety analyses will include assessments of adverse events, vital signs, electrocardiograms and laboratory parameters.

An independent Data Monitoring Committee will be used to monitor unblinded safety data.

2. Schedule of Activities

Table 2-1. Schedule of Activities

Study Day	S ^a	Treatment						Completion or Hospital Discharge or ED ^{b,c}	Follow-Up Phone Visit 1 ^d	Follow-Up Phone Visit 2 ^d
	≤1	1	2	7	15	16	21	28 (or the day discharged from hospital or ED)	42 ^d	60
Window Period (days)		-	-	±2	-	-	±2	±1	±2	±2
Eligibility review	X									
Informed consent	X									
Demographics	X									
Medical history ^e	X									
Height	X									
Weight	X							X		
Physical examination (directed unless otherwise noted)	X (complete)	X		X	X		X	X (complete)		
Vital signs ^f	X	← Every day from Day 1 to 27 → Predose and postdose on Days 1 and 15						X		
Hematology and clinical chemistry		X (pre-dose) ^g	X	X	X (pre-dose)	X	X	X		
COVID-19 panel ^h		X (pre-dose)	X	X		X	X	X		
Influenza/RSV/respiratory viral panel ⁱ		X								
Thyroid function test (TSH and FT4)		X (pre-dose)						X		
Pregnancy Test ^j	X (serum / urine)							X (urine)		
12-Lead ECG ^k		X (pre-and post-dose) ^l			X (pre-and post-dose)			X		

	S ^a	Treatment						Completion or Hospital Discharge or ED ^{b,c}	Follow-Up Phone Visit 1 ^d	Follow-Up Phone Visit 2 ^d
Study Day	≤1	1	2	7	15	16	21	28 (or the day discharged from hospital or ED)	42 ^d	60
Window Period (days)		-	-	±2	-	-	±2	±1	±2	±2
Randomization ^m		Within 24 hours of screening								
Study drug administration ⁿ		Within 8 hours of randomization			X					
SpO ₂ , O ₂ flow rate ^o	X	← Every day from Day 1 to 27 →						X		
NIAID ordinal assessment ^p	X	← Every day from Day 1 to 27 →						X	X	X
Adverse event monitoring ^q		← Every day from Day 1 to 27 →						X	X	X
Supportive pulmonary care ^r		← Every day from Day 1 to 27 →						X		
Concomitant medications ^s		← Every day from Day 1 to 27 →						X		

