4.13.3 Clinical Laboratory Evaluation

Blood samples for hematology and clinical chemistry will be collected. Profiles for the hematology, clinical chemistry will be summarized, and patients with values outside the normal range during the on-treatment period during the study will be summarized.

Change from baseline for each of the hematology, clinical chemistry will be derived for each of the post-dose time points using the pre-dose measurement as the baseline. Descriptive statistics for the measurement at baseline and the measurement and change from baseline at each postdose time point will be tabulated.

Laboratory results recorded as " $< x$ " or " $\leq x$ " will be imputed as x ; results recorded as " $> x$ " or " $\geq x$ " will be imputed as x and a footnote will be added to indicate the number of patients and visits that were above the limit.

Each laboratory parameter will be classified as low, normal or high relative to the central laboratory’s normal range. For each treatment group shift tables will be generated from the predose category to the category post-dose for each laboratory parameter. The shift tables will present the number (percent) of patients who started in a category (low, normal, high) at baseline and ended in a category at each scheduled visit before the end of the study. A missing category will be included for both pre-dose and post-dose, so that all patients in the Safety population will

be represented in the table. The missing category includes the cases where the normal range is partially or completely missing, the unit of measurement is missing, and/or the laboratory result itself is missing. The percentages will be calculated using number of patients in the Safety population who have measurements at pre-dose and post-dose.

Shift tables comparing pre-dose to the other time points in the study may be generated if warranted after data review.

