4.13.4 Vital Signs

Extreme vital signs will be determined using the following criteria:

- Heart rate either < 50 bpm or > 100 bpm,
- Systolic blood pressure either ≤ 90 mmHg or ≥ 160 mmHg,
- Diastolic blood pressure either ≤ 50 mmHg or ≥ 100 mmHg.

The number (percent) of patients having extreme vital signs will be tabulated by treatment group at each scheduled visit. The percentage will be calculated using the number of patients in the Safety population with data at each visit as the denominator. The number (percent) of patients having extreme vital signs post-baseline (including unscheduled assessments) will be calculated.

Change from baseline statistics will also be defined for the measurements of blood pressure, heart rate and temperature using the pre-dose values as baseline. Descriptive statistics for the measurement of temperature will also be provided by treatment group.

All patients who have an extreme vital sign value will be documented in a by-patient listing. The listing will include all of the vital sign measurements from the study for the patient, and the extreme values will be flagged.

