4.13.5 Electrocardiograms

The number (percent) of patients who had an abnormal ("Abnormal, CS" or "Abnormal, NCS") ECG at any time while on-treatment will be tabulated by treatment group. All on-treatment ECGs, including unscheduled assessments, will be considered.

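### The SAP gives no rule for unscheduled laboratory results and no by-arm count of patients by peak liver-test value; its three-category shift tables can hide a marked rise

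*Protocol*

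**What the plan says.** **Collection.** Protocol Table 2-1 schedules hematology and clinical chemistry on Days 1, 2, 7, 15, 16, 21 and 28 (or discharge or early discontinuation). Appendix 2 includes ALT, AST, alkaline phosphatase and total and direct bilirubin. A footnote to the Appendix 4 sampling table adds that "Based on laboratory safety values, unscheduled hepatic monitoring testing may be performed as part of patient follow-up", in consultation with the medical monitor. It is permissive and states no trigger.

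**Analysis.** SAP 4.13.3 plans three things for chemistry:
- descriptive statistics for the value and the change from baseline at each post-dose time point (Table 16), which SAP 4.1 defines as n, mean, SD, median, minimum and maximum;
- a summary of patients with any on-treatment value outside the normal range (Table 20);
- shift tables (Tables 17–18). For these, "Each laboratory parameter will be classified as low, normal or high relative to the central laboratory" range, and patients are counted by how they "started in a category (low, normal, high) at baseline and ended in a category at each scheduled visit before the end of the study". Shift tables at other time points are optional after data review.

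**Contrast.** For vital signs (SAP 4.13.4): "The number (percent) of patients having extreme vital signs post-baseline (including unscheduled assessments) will be calculated". For ECGs (SAP 4.13.5): "All on-treatment ECGs, including unscheduled assessments, will be considered". SAP 4.13.3 has no matching sentence.

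**The concern.** The protocol foresees targeted extra testing in one laboratory area, the liver, and the SAP does not say what is done with those results. They have no visit slot in a by-visit table, and the shift tables are tied to scheduled visits.

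The three categories are a separate limit. Above the upper limit there is only one category, so a patient who starts slightly high and ends many times higher is counted as high-to-high. The eligibility criteria set no aminotransferase limit, so such patients can be enrolled.

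At stake is whether the final report can state, by arm, how many patients had a marked liver-test rise. Safety is a stated objective. The DMC package listed in SAP 4.16 contains no laboratory table, and the sponsor's ongoing laboratory monitoring is blinded, so the final by-arm tables carry most of this comparison.

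**Working it through.** **1. Do the extra hepatic tests fit the planned visits?** Table 2-1 has 7 scheduled hematology and chemistry draws. Appendix 4 gives a maximum of 7 samples of 3–6 mL: 7 × 3 = 21 mL and 7 × 6 = 42 mL, which matches its 21–42 mL. The maximum therefore covers the scheduled draws only. Unscheduled hepatic tests come on top and have no assigned place.

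**2. What does each planned output show about a marked rise?**

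| Output | Shows | Does not show |
|---|---|---|
| Table 16 | Mean, SD, median, minimum, maximum by study day | How many patients had a marked rise; any patient's peak over the study |
| Table 18 | Low/normal/high at scheduled visits | Any rise within the high category; unscheduled values |
| Table 20 | Patients with an out-of-range value on treatment | Size of the excursion |
| Table 11 | TEAEs by maximal CTCAE severity | Rises not recorded as AEs |
| Listings 14–15 | Individual results | A by-arm summary |

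The Table 16 maximum is one patient's value on one study day. It cannot tell one patient with a marked rise from ten.

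**3. How much can an any-abnormal count dilute a signal?** This is an illustration; the documents give no rates. Assume ALT of at least 5 × the upper limit in 2% on placebo and 10% on drug. Assume a fraction e of placebo patients have ALT above normal at some time, and the extra 8% on drug occur independently of that. Then any-abnormal on drug = e + (1 − e) × 0.08. Power is for the pooled z-test, by exact binomial enumeration, 100 per arm, one-sided 0.05.

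| Summary | Placebo | Drug | Power |
|---|---|---|---|
| Graded count, ≥5 × limit | 2% | 10% | 82.4% |
| Any abnormal, e = 0.45 | 45% | 0.45 + 0.55 × 0.08 = 49.4% | 15.7% |
| Any abnormal, e = 0.30 | 30% | 0.30 + 0.70 × 0.08 = 35.6% | 21.4% |
| Any abnormal, e = 0.60 | 60% | 0.60 + 0.40 × 0.08 = 63.2% | 11.6% |
| Graded count, smaller contrast | 2% | 6% | 46% |
| Graded count, smaller contrast | 2% | 5% | 35% |

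**4. How often would scheduled draws catch a short episode?** Assume onset equally likely on each of Days 2–14 (13 start days), the patient still in hospital, and draws on Days 2, 7, 15, 16 and 21. Count the start days for which the episode covers a draw.

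| Episode length (days) | Start days caught |
|---|---|
| 2 | 4/13 = 31% |
| 3 | 6/13 = 46% |
| 4 | 8/13 = 62% |
| 5 | 10/13 = 77% |
| 7 | 12/13 = 92% |
| 10 | 13/13 = 100% |

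The result turns entirely on the assumed duration, which the documents do not give.

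**The case against.** The strongest reply is that the SAP already reports liver values by arm, and much of it stands.

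- A reader might infer that the size of liver-test rises is never compared by arm. The documents do not support that. Table 16 gives value and change by study day, SAP 4.13 has laboratory changes summarized by treatment group, and a large value at a scheduled draw raises that arm's SD and maximum.
- A reader might infer that unscheduled results are excluded throughout. They are not; their use is unstated. The text behind Table 20 covers the on-treatment period and is not limited to scheduled visits. Only the shift tables are so limited.
- A reader might infer from Protocol 9.4.3 that only rises leading to a diagnosis reach the AE tables. Protocol Appendix 1 counts an abnormal laboratory finding as a possible AE, and SAP 4.13.2 grades every AE by CTCAE. A recorded ALT increase would therefore appear in Table 11. That route still depends on the investigator choosing to record it.
- The power figures do not measure a failed test, because the laboratory summaries are descriptive. The 2% v 10% contrast is assumed, and smaller contrasts give much less.
- The capture figures fit Appendix 4 poorly. The extra tests follow from laboratory values, so they track a rise already seen rather than search for one between visits.
- The documents flag no hepatic signal; the named AE of special interest is secondary infection.

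What the reply does not supply is a rule for unscheduled laboratory results, a per-patient peak, or any grading above the upper limit in a by-arm laboratory table.

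**Conclusion.** The point holds as a gap in the laboratory safety summaries. SAP 4.13.3 reports liver values by study day and arm and counts any abnormality. It does not say whether unscheduled results count, and it plans no by-arm laboratory table of how many patients reached a given peak. A marked rise in a patient already high at baseline is invisible in the shift tables.

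This rests on the wording of SAP 4.13.3 and the table list, not on the illustrative figures. Those show only that an any-abnormal count can dilute a signal that a graded count would show more clearly. Its size in this trial cannot be derived from the documents. Nothing here affects the efficacy analyses or implies that a liver effect exists. The change is worth making because it is cheap and gives a better safety summary than the stated rule.

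**What to change.** In SAP 4.13.3 and Tables 17–18:

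1. State that unscheduled laboratory results recorded in the database count in the per-patient summaries, as the SAP already does for vital signs and ECGs, and say whether they count in Table 20.
2. Add a by-arm, per-patient shift from baseline to worst post-dose value for ALT, AST, alkaline phosphatase and total bilirubin. Use prespecified multiples of the reporting laboratory's upper limit (for example ≤1, >1–3, >3–5, >5–10, >10) or CTCAE v5.0 grade.
3. Keep the scheduled-visit tables alongside it.

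**Cost.** SAP wording and one table layout; no new visit or sample. Confirm that unscheduled hepatic results are entered in the eCRF, since the documents do not say so.

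**Downside.** Patients tested more often have more chances of an extreme value. Blinding of investigators (Protocol 7.3) limits bias from knowledge of treatment, but not a difference in testing that follows from the values themselves. The scheduled-visit tables serve as the check.
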